## 1 Study Subjects, Demographics, and Other Baseline Characteristics

### 1.1 Disposition of Subjects

#### 1.1.1 Study Information in This Study

Analysis Set: All Subjects Who Signed the Informed Consent Form in This Study

Analysis Variable(s): Date First Subject Signed Informed Consent Form in This Study  
Date of Last Subject's Last Visit/Contact in This Study  
MedDRA Version in this study  
WHO Drug Version in this study  
SAS Version Used for Creating the Data Sets in This Study

Analysis Method(s): The following analysis will be performed for the above analysis variables.  
(1) Display of analysis variables

#### 1.1.2 All Subjects Who Did Not Enter the Treatment Period

Analysis Set: All Subjects Who Did Not Enter the Treatment Period Among the Subjects Who Signed the Informed Consent Form in This Study

Analysis Variable(s): Categories in parentheses (hereinafter the same)  
Age (years) [Min<= - <65, 65<= - <=Max]  
Gender [Male, Female]

Analysis Method(s): The following analysis will be performed for the above analysis variables.  
(1) Frequency distributions for categorical variables and descriptive statistics for continuous variables

#### 1.1.3 Subject Eligibility in This Study

Analysis Set: All Subjects Who Signed the Informed Consent Form in This Study

Analysis Variable(s): Status of Entrance into This Study [Yes, No]  
Reason for Not Entering to This Study [Pretreatment Event/Adverse Event, Significant Protocol Deviation, Lost to Follow-up, Voluntary Withdrawal, Study Termination, Did Not Meet Entrance Criteria or Violation of Exclusion Criteria, Other]

Analysis Method(s): The following analysis will be performed for the above analysis variables.  
When calculating percentages for the primary reasons for subject not entering to this study, the total number of subjects who did not enter this study will be used as the denominator.  
(1) Frequency distributions

#### 1.1.4 Number of Subjects Who Entered This Study in Each Site

Analysis Set: All Subjects Who Entered This Study

Analysis Variable(s): Status of Entrance into This Study [Yes]

Stratified Variable(s): Site [Site numbers will be used as categories]

Analysis Method(s): The following analysis will be performed for the above analysis variables by treatment group in the preceding study for each stratified item and by combining the treatment groups in the preceding study.  
(1) Frequency distributions

### 1.1.6 Study Drug Completion Status

#### 1.1.6.1 Assessment of This Study

Analysis Set:	All Subjects Who Entered This Study
Analysis Variable(s):	Study Drug Completion Status in This Study [Completed Study Drug, Prematurely Discontinued Study Drug]
	Reason for Discontinuation of Study Drug [Pretreatment Event/Adverse Event, Significant Protocol Deviation, Lost to Follow-up, Voluntary Withdrawal, Study Termination, Pregnancy, Lack of Efficacy, Other]
Categories:	Duration of study drug administration in this study (days) [0, 1<= - <28, 28<= - <56, 56<= - <84, 84<= - <112, 112<= - <140, 140<= - <168, 168<= - <=Max]
Analysis Method(s):	The following analysis will be performed for the above analysis variables by treatment group in the preceding study and by combining the treatment groups in the preceding study. (1) Frequency distributions by treatment period of study drug in this study

### 1.1.6.2 Assessment of Preceding Study and This Study

Analysis Set: All Subjects Who Were Randomized in the Preceding Study

Analysis Variable(s): Study Drug Completion Status for the Treatment Period in Both Studies  
 [Completed Study Drug, Prematurely Discontinued Study Drug]

Reason for Discontinuation of Study Drug  
 [Pretreatment Event/Adverse Event, Significant Protocol Deviation, Lost to Follow-up, Voluntary Withdrawal, Study Termination, Pregnancy, Lack of Efficacy, Other]

Categories: Duration of study drug administration for the treatment period in both studies (days)  
 [0, 1<= - <84, 84<= - <168, 168<= - <252, 252<= - <336, 336<= - <=Max]

Analysis Method(s): The following analysis will be performed for the above analysis variables by treatment group in the preceding study and by combining the treatment groups in the preceding study.  
 (1) Frequency distributions by treatment period of study drug administration for the treatment period in both studies

### 1.1.7 Protocol Deviations and Analysis Data Set

#### 1.1.7.1 Protocol Deviations

Analysis Set: All Subjects Who Entered This Study

Analysis Variable(s): Protocol Deviations  
 [Major GCP Violations, Deviations of Protocol Entry Criteria, Deviations of Discontinuation Criteria, Deviations Related to Treatment Procedure or Dose, Deviations Concerning Excluded Medication or Therapy, Deviations to Avoid Emergency Risk, Other Deviation]

Analysis Method(s): The following analysis will be performed for the above analysis variables by treatment group in the preceding study and by combining the treatment groups in the preceding study.  
 The number of subjects with protocol deviations will be calculated and the details of deviations will be shown after classifying the contents of deviations into the above categories. A subject who has several categories will be counted once in each appropriate category.  
 (1) Frequency distributions

#### 1.1.7.2 Analysis Sets

Analysis Set: All Subjects Who Were Randomized in the Preceding Study

Analysis Variable(s): Handling of Cases in Analysis Sets and Case Data  
 [Categories are based on the specifications in “Handling Rules for Analysis Data”]

Inclusion/Exclusion of Analysis Set

Analysis Method(s):	Full Analysis Set	[Included]
	Full Analysis Set 2	[Included]
	Safety Analysis Set	[Included]
The following analyses (1) and (2) will be performed for the above analysis variables by treatment group in the preceding study and the following analysis (3) will be performed by treatment group in the preceding study and by combining the treatment groups in the preceding study.		
For (1) and (2), a subject who has several categories will be counted once in each appropriate category.		
(1) Frequency distributions for handling of cases in each analysis set		
(2) Frequency distributions for handling of case data in each analysis set		
(3) Frequency distributions for number of cases included in each analysis set		

## 1.2 Demographic and Other Baseline Characteristics

### 1.2.1 Summary of Demographics and Other Baseline Characteristic

Analysis Set:	Safety Analysis Set	
Analysis Variable(s):	Age (years)	[Min<= - <65, 65<= - <=Max]
	Gender	[Male, Female]
	Height (cm)	
	Weight (kg) (Baseline (prior to TVP-1012 administration))	
	BMI(kg/m  )	
	Smoking history	[The subject has never smoked, The subject is a current smoker, The subject is an ex-smoker]
	Timing of Study Drug Administration	[Before breakfast, After breakfast]
	Duration of Parkinson's disease (years)	[Min<= - <1.5, 1.5<= - <=Max]
	Modified Hoehn and Yahr Scale	[Min<= - <2.0, 2.0<= - <3.0, 3.0<= - <=Max]
	MDS-UPDRS Part II + Part III total score (Baseline (prior to TVP-1012 administration))	
Analysis Method(s):	The following analysis will be performed for the above analysis variables by treatment group in the preceding study and by combining the treatment groups in the preceding study.	
	(1) Frequency distributions for categorical variables and descriptive statistics for continuous variables	

### 1.2.2 Medical History and Concurrent Medical Conditions

Analysis Set:	Safety Analysis Set	
Analysis Variable(s):	Medical History in the Preceding Study	
	Concurrent Medical Conditions in the Preceding Study	
Analysis Method(s):	The following analysis will be performed for the above analysis variables by treatment group in the preceding study and by combining the treatment	

groups in the preceding study.

MedDRA dictionary will be used for coding. Summaries will be provided using SOC and PT, where SOC will be sorted alphabetically and PT will be sorted in decreasing frequency.

- (1) Frequency distributions for medical history in the preceding study (by SOC/PT)
- (2) Frequency distributions for concurrent medical conditions in the preceding study (by SOC/PT)

The method of counting events when conducting each frequency distribution will be as follows:

[Number of subjects with medical history and/or concurrent medical conditions]

A subject with multiple occurrences of medical history or concurrent medical conditions within a SOC will be counted only once in that SOC.

A subject with multiple occurrences of medical history or concurrent medical conditions within a PT will be counted only once in that PT.

### 1.2.3 Medication History and Concomitant Medications

Analysis Set: Safety Analysis Set

Analysis Variable(s): Medication History in the Preceding Study

Concomitant Medications in the Preceding Study and This Study

Analysis Method(s): The following analysis will be performed for the above analysis variables by treatment group in the preceding study and by combining the treatment groups in the preceding study.

The WHO Drug dictionary will be used for coding. Summaries will be provided using Preferred Names and sorted in decreasing frequency based on the number of reports.

A subject who has been administered multiple doses of the same medication (Preferred Name) will be counted only once for that medication (Preferred Name).

- (1) Frequency distributions for medication history in the preceding study
- (2) Frequency distributions for concomitant medications that the subject started to use prior to study drug administration for the treatment period in the preceding study and also used during the treatment period, and concomitant medications that the subject started to use after study drug administration for the treatment period in the preceding study

## 1.3 Measurements of Treatment Compliance

### 1.3.1 Exposure and Compliance of TVP-1012

Analysis Set: Safety Analysis Set

Analysis Variable(s): Duration of Exposure to TVP-1012 (days) [1<= - <84, 84<= - <168, 168<= - <252, 252<= - <336, 336<= - <=Max]  
Compliance of TVP-1012 (%) [Min<= - <50.0, 50.0<= - <70.0, 70.0<= - <90.0, 90.0<= - <=Max]

Analysis Method(s): The following analysis will be performed for the above analysis variables

by treatment group in the preceding study and by combining the treatment groups in the preceding study.

- (1) Frequency distributions for categorical variables and descriptive statistics for continuous variables

## 2 Efficacy Analysis

### 2.1 Secondary Endpoint and Analytical Method

#### 2.1.1 MDS-UPDRS Part II + Part III Total Score

##### 2.1.1.1 Analysis based on the data after administration of TVP-1012

Analysis Set: Full Analysis Set

Analysis Variable(s): MDS-UPDRS Part II + Part III total score

Visit: Baseline (prior to TVP-1012 administration), Week 6, Week 10, Week 14, Week 20, Week 26, Week 32, Week 36, Week 40, Week 46, Week 52, End of Treatment

Analysis Method(s): Descriptive statistics and two-sided 95% confidence intervals of means at each visit by treatment group in the preceding study will be provided for the MDS-UPDRS Part II + Part III total score at each visit and the change from baseline (prior to TVP-1012 administration) in the MDS-UPDRS Part II + Part III total score at each visit of the treatment period (at each visit during the treatment period (Week 6 to End of Treatment)-Baseline (prior to TVP-1012 administration)). Furthermore, the means and standard deviations by treatment group in the preceding study will be shown in graphical display for the MDS-UPDRS Part II + Part III total score at each visit, and the change from baseline (prior to TVP-1012 administration) in the MDS-UPDRS Part II + Part III total score at each visit of the treatment period.

##### 2.1.1.2 Analysis based on the data after study drug administration for the treatment period in the preceding study

Analysis Set: Full Analysis Set 2

Analysis Variable(s): MDS-UPDRS Part II + Part III total score

Visit: Baseline (at end of observation period), Week 6, Week 10, Week 14, Week 20, Week 26, Week 32, Week 36, Week 40, Week 46, Week 52 of Treatment Period, Week 52 of Treatment Period (LOCF)

Analysis Method(s): The same analysis as 2.1.1.1 will be performed for the above analysis variables. Furthermore, the point estimates of the mean differences between treatment groups (1 mg → 1 mg group-P → 1 mg group) and the two-sided 95% confidence intervals at each visit by treatment group in the preceding study will be provided for the change from baseline (at end of observation period) in the MDS-UPDRS Part II + Part III total score at each visit during the treatment period (at each visit during the treatment period (Week 6 to Week 52 of Treatment Period (LOCF))-Baseline (at end of observation period)).

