6.2.4 Justification for Treatment Period

Parkinson's disease is a progressive disease and long-term administration is anticipated when TVP-1012 is prescribed. Therefore, another 26-week extension of treatment was planned following the 26-week treatment in the preceding study to evaluate the long-term safety of TVP-1012 for 6 months and 12 months.

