13.1.3 Efficacy Analysis

(1) [Secondary endpoint and its analytical method]

[Secondary endpoint]

- MDS-UPDRS Part II + Part III total score

[Analysis method]

CONFIDENTIAL

The following analysis will be performed for FAS.

Descriptive statistics (number of subjects, mean, standard deviation, maximum, minimum, and quartiles) and two-sided 95% confidence intervals of means will be provided for the MDS-UPDRS Part II + Part III total score at each visit and the change from baseline in the MDS-UPDRS Part II + Part III total score at each visit of the treatment period by treatment group in the preceding study.

(2) Additional efficacy endpoints

Refer to Section 5.2.3.

(3) Method of data conversion and handling of missing data

Details will be described in the Handling Rules for Analysis Data and the Statistical Analysis Plan.

(4) Significance level and confidence coefficient

- Confidence coefficient: 95% (two-sided)

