13.3 Determination of Sample Size

Number of subjects to be enrolled in this study: approximately 182

[Justification of Sample size]

In the preceding study, the planned number of subjects to be randomized was a total of 240 (120 per group) and the planned number of subjects evaluable for the primary endpoint (change in the MDS-UPDRS Part II + Part III total score from baseline to Week 26 of the treatment period (LOCF)) was a total of 220 (110 per group).

Since this study is a long-term extension study in patients with early Parkinson's disease who have completed the 26-week treatment period in the preceding study, considering the potential dropouts in the preceding study, approximately 182 subjects will be enrolled in this study.

In addition, considering the potential dropouts in this study and in the preceding study, it is estimated that 155 subjects will be treated with 1 mg of TVP-1012 for 26 weeks and 59 subjects for 52 weeks.

CONFIDENTIAL

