## **2.3 Statistical/Analytical Issues**

### **2.3.1 Adjustments for Covariates**

Not applied in this study.

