**4 Significance Level and Confidence Coefficient**

- Confidence coefficient: 95% (two-sided)

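### The between-group difference in MDS-UPDRS Part II + III change is estimated without the baseline score as covariate: valid under randomisation, but generally less precise than a baseline-adjusted estimate

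*SAP*

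**What the plan says.** SAP 2.1.1.2 analyses Full Analysis Set 2, with time counted from the start of treatment in the preceding study. In addition to the summaries by group, it calls for "the point estimates of the mean differences between treatment groups" (1 mg → 1 mg minus P → 1 mg) with two-sided 95% confidence intervals. The outcome is the "change from baseline (at end of observation period) in the MDS-UPDRS Part II + Part III total score at each visit during the treatment period", and a Week 52 (LOCF) row is added. No model or covariate is named.

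SAP 2.3.1, on covariate adjustment, reads "Not applied in this study" and gives no reason. The other efficacy sections (2.1.1.1, 2.2.1, 2.2.2, 2.3.8.1) give summaries within groups only, so 2.1.1.2 holds the SAP's only between-group efficacy estimate.

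Protocol 13.1.3 asks for less. It says that descriptive statistics and "two-sided 95% confidence intervals of means will be provided for the MDS-UPDRS Part II + Part III total score at each visit", and for the change from baseline, by preceding-study group. The between-group contrast was added in the SAP.

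**The concern.** The groups come from the preceding study's randomisation, so leaving out the covariate does not bias the comparison. What is lost is precision. A change score assumes that one point more at baseline means exactly one point more at follow-up. When the true slope is not 1, the raw difference carries baseline noise that a regression on baseline would remove. The covariate costs nothing to obtain, since every subject with a change value has a baseline score.

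At stake is the width of the interval around the one efficacy contrast between the two groups. Up to Week 26 that contrast is active against placebo. From then on it is early against delayed start, since Protocol 6.2.3 puts both groups on 1 mg.

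**Working it through.** **Inputs from the documents.** The preceding study planned 240 randomised (120 per group) and 220 evaluable at Week 26 with LOCF (110 per group) (Protocol 13.3). The confidence level is 95%, two-sided (SAP section 4). The plan states no SD, correlation, effect size or target width for this comparison, so it has no figure to reproduce.

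**Assumptions.** ρ is the correlation between baseline and follow-up score. k is follow-up SD divided by baseline SD. Both are varied. Values of k above 1 are included because Protocol 6.2.4 notes that "Parkinson's disease is a progressive disease", and spread may grow over time.

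**Formulas**, with baseline SD = 1 and each variance multiplied by (1/n₁ + 1/n₀):

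- Raw change: V_raw = 1 + k² − 2ρk
- ANCOVA (large sample): V_adj = k²(1 − ρ²)
- Difference: V_raw − V_adj = (1 − ρk)², which is never negative and is zero only when the slope ρk equals 1
- Ratio of interval widths: √(V_adj / V_raw)

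| k | ρ | V_raw | V_adj | Variance ratio | Width ratio | Narrower by |
|---|---|---|---|---|---|---|
| 1.0 | 0.5 | 1.00 | 0.75 | 0.750 | 0.866 | 13.4% |
| 1.0 | 0.7 | 0.60 | 0.51 | 0.850 | 0.922 | 7.8% |
| 1.0 | 0.8 | 0.40 | 0.36 | 0.900 | 0.949 | 5.1% |
| 1.0 | 0.9 | 0.20 | 0.19 | 0.950 | 0.975 | 2.5% |
| 1.2 | 0.5 | 1.24 | 1.080 | 0.871 | 0.933 | 6.7% |
| 1.2 | 0.7 | 0.76 | 0.734 | 0.966 | 0.983 | 1.7% |
| 1.2 | 0.8 | 0.52 | 0.518 | 0.997 | 0.998 | 0.2% |
| 1.2 | 0.9 | 0.28 | 0.274 | 0.977 | 0.989 | 1.1% |

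**Cost of estimating the slope.** With N = 220, V_adj is multiplied by 1 + 1/(N − 4) = 1 + 1/216. At k = 1 the width ratios become 0.868, 0.924, 0.951 and 0.977, so the cost is negligible. In baseline SD units, with 110 per group, the 95% half-width falls from 0.264 to 0.229 at ρ = 0.5, from 0.205 to 0.189 at 0.7, and from 0.118 to 0.115 at 0.9. For equal precision the raw estimate would need about 33%, 17% and 5% more patients.

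**Simulation** (4,000 trials per setting, complete data, 110 per group). At k = 1 and ρ = 0.5, 0.7 and 0.9, the bias of the raw estimate was at most 0.003 SD and its interval coverage was 94.5% to 95.4%, which supports calling it valid. The SE ratios, adjusted to raw, were 0.866, 0.915 and 0.979. With ρ = 0.8 and k = 1.25 (slope exactly 1) the ratio was 1.002, so there was no gain.

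**Chance imbalance.** With 110 per group, the SE of the baseline difference is √(2/110) = 0.135 SD. After an imbalance of that size, the raw difference keeps (slope − 1) × 0.135, that is −0.067, −0.040, −0.027 and −0.013 SD at slopes of 0.5, 0.7, 0.8 and 0.9. This is not a second loss. Its variance, (1 − ρk)² × 2/110, is exactly the excess variance derived above.

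No Week 52 width is given. The 59 subjects with 52 weeks on 1 mg in Protocol 13.3 can only be the 1 mg → 1 mg group, and the other group's number is not stated.

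**The case against.** The strongest reply is that nothing is broken. The estimate is valid, adjustment was considered and declined in 2.3.1, the primary endpoint is adverse events, and the contrast goes beyond what Protocol 13.1.3 requires. No test, target width or sample size depends on it. All of this stands, and it keeps the point at the level of a suggestion.

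The gain also rests wholly on assumed values of ρ and k. The 13% arises only at the corner ρ = 0.5, k = 1. At k = 1.2 the gain is below 2% for ρ from 0.7 to 0.9. Protocol 9.1.13 asks for certified evaluators and, in principle, the same evaluator per subject, which favours a higher ρ. This limits the size of the gain but not its direction: ANCOVA gives up almost nothing in the unfavourable cases.

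The imbalance figures correspond to k = 1. At k = 1.2 the slopes are 0.60, 0.84, 0.96 and 1.08, and the carry-over is −0.054, −0.022, −0.005 and +0.011 SD. That is correct, and the effect is small either way.

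Finally, validity here means validity of the randomised comparison. After Week 26 only those who entered the extension contribute observed values, about 182 of the planned 240. Adjustment is no general remedy for that selection. It can deal only with the part that the baseline score explains. In an illustrative simulation with assumed baseline-dependent dropout in one arm, the raw difference was biased by 0.02 to 0.09 SD and the adjusted one was essentially unbiased. This is a separate missing-data question.

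**Conclusion.** The point holds as a matter of efficiency, not of error. The planned difference and its interval are valid under randomisation but generally less precise than ANCOVA on the baseline score. The interval would be about 0% to 13% narrower for ρ of 0.5 to 0.9 and k of 1.0 to 1.3, with almost no gain where ρk is near 1. The half-widths and imbalance figures also assume that Full Analysis Set 2 is close to 110 per group. Its definition is in the Handling Rules for Analysis Data, which were not available. For a secondary endpoint with no test attached, the change is worth considering but not essential.

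**What to change.** In SAP 2.1.1.2, estimate the group difference in change at each visit and at Week 52 (LOCF) by ANCOVA, with preceding-study treatment group as factor and the MDS-UPDRS Part II + III score at the end of the observation period as covariate. Report adjusted means, the difference and its two-sided 95% interval. Keep the raw means and differences as a descriptive display, so that Protocol 13.1.3 is still met. Amend 2.3.1 to name the covariate.

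The cost is a text change in two sections and one standard model per visit, with one degree of freedom each and no new data. A repeated-measures model with baseline-by-visit terms is an alternative for the visit-wise estimates. It would also need a stated covariance structure, and it changes how incomplete subjects contribute compared with SAP 2.3.2.

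Fix the covariate before database lock. The documents do not say whether the preceding study's data, which supply Weeks 6 to 26, were already unblinded when the SAP was written. If they were, the SAP should say so. If the sponsor prefers no adjustment, one line of justification in 2.3.1 would be the minimum.

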## 2.2 Other Endpoints and Analytical Methods

### 2.2.1 MDS-UPDRS Total Scores and Individual Scores

Analysis Set: Full Analysis Set

Analysis Variable(s): MDS-UPDRS Part I total score  
MDS-UPDRS Part II total score  
MDS-UPDRS Part III total score  
MDS-UPDRS Part IV total score

MDS-UPDRS tremor score	
MDS-UPDRS bradykinesia score	
MDS-UPDRS muscle rigidity score	
MDS-UPDRS individual scores	
Visit:	Baseline (prior to TVP-1012 administration), Week 6, Week 10, Week 14, Week 20, Week 26, Week 32, Week 36, Week 40, Week 46, Week 52, End of Treatment
Analysis Method(s):	The same analysis as 2.1.1.1 will be performed for the above analysis variables. However, the graphical display of the mean and standard deviation is excluded.

